Co-investigators	
[name] University of Warwick [contact]
 
Associate [name] University of Warwick/University of Birmingham [contact]/[contact]
 
[name] University of Warwick/University of Birmingham [contact]/[contact]
 
[name] University of Warwick [contact]
 
[name] University of Warwick [contact]
 
[name] University of Warwick [contact]
 
[name] Kings College Hospital NHS Foundation Trust [contact]
 
[name] Hull University Teaching Hospitals NHS Trust [contact]
 
[name] County Durham and Darlington NHS Foundation Trust [contact]
 
[name] University of Warwick

	
[contact]
 
[name] University of Warwick/University of Birmingham [contact]/[contact]
 
[name] PPI Representative
 
[name] PPI Representative
 
[name] PPI Representative

Sponsor	
[name] Research and Development Department UHCW NHS Trust [name] [contact] [contact]

Funder	
National Institute for Health Research (NIHR) [name] [contact]

Trial Co-ordination Centre	
[name] Trial Manager UHCW NHS Trust [name] [contact] [contact]

STUDY SUMMARY

Full study title	SUMU-Endo: Single-use versus Multiple-use Endoscopes in Gastroenterology: Multi methods analysis to balancing infection control and environmental impact
Short study title	SUMU-Endo
Study aim	To explore the views and experiences of patients receiving endoscopy and staff involved in procuring, using, cleaning and decontaminating endoscopes.
Study design	A multi-centre mixed-methods qualitative study using interviews and focus groups.
Study participants	Patients who have had an endoscopy in the NHS. NHS staff involved in supply chain, decontamination of endoscopes.
Planned Size of Sample	30 NHS Patients 30 NHS Staff
Planned Study period	18 months
Planned recruitment start date	01 Aug 2024
Planned recruitment end date	30 September 2025
Planned study end date	31 December 2025
Objectives	
Patient interviews
 
1. To explore the views and experiences of patients receiving endoscopy in the NHS
 
Staff focus groups/interviews
 
1. To explore the views and experiences of staff involved in procuring, using, cleaning and decontaminating endoscopes in the NHS.

STUDY FLOW CHART

[figure not shown]

Figure 1: Flow of participants through the study

SCHEDULE OF EVENTS

Table 1: Schedule of Events

Procedure	Screening	Visit 1 – in person	Visit 1 – remotely
Eligibility assessment	X		
Informed consent		X	X*
Type of endoscopy procedure and type of endoscope	X*		
Demographic data	X	X	X
Participate in Focus Group/Interview		X	X

*patients only.

Contents

SIGNATURE PAGE	2
KEY STUDY CONTACTS	3
STUDY SUMMARY	5
STUDY FLOW CHART	6
SCHEDULE OF EVENTS	7
LIST OF ABBREVIATIONS	10
1. INTRODUCTION	11
1.1 Background	11
1.2 Justification.....	13
1.3 Proposed study.....	14
1.4 Study population.....	14
2 OBJECTIVES.....	14
2.1 Primary objective	14
2.2 Primary outcome measures.....	14
3 STUDY DESIGN AND METHODS OF DATA COLLECTION AND ANALYSIS	14
3.1 Study Design and Data Collection	14
3.2 Data Analysis	16
4. STUDY SETTING.....	17
5. ELIGIBILITY CRITERIA	17
5.1 Inclusion criteria.....	17
5.2 Exclusion criteria	18
6. STUDY PROCEDURES.....	18
6.1 Sampling	18
6.2 Size of sample	18
6.3 Recruitment.....	18
6.4 Consent.....	19
6.5 Site Staff Training.....	19
6.6 End of study	20
7. DATA MANAGEMENT	20
7.1 Data collection and management	20
7.2 Data storage.....	21
7.3 Data access.....	21
7.4 Archiving	21

8. STUDY OVERSIGHT	21
8.1 Role and responsibilities of the Sponsor	21
8.2 Role and responsibilities of the Funder	22
8.3 Trial Management Arrangements	22
8.3.1 Trial Coordination	22
8.3.2 Principal Investigators.....	22
9. MONITORING, AUDIT & INSPECTION	22
10. ETHICAL AND REGULATORY CONSIDERATIONS.....	23
10.1 Ethical approval and research governance.....	23
10.2 Peer review	23
10.3 Public and Patient Involvement.....	23
10.4 Assessment and management of risk.....	24
11. DISSEMINATION POLICY	24
12. REFERENCES	25

LIST OF ABBREVIATIONS

CI	Chief Investigator
CRF	Case Report Form
ED&I	Equality, Diversity & Inclusion
EU	European Union
GCP	Good Clinical Practice
GI	Gastrointestinal
GP	General Practitioner
HRA	Health Research Authority
ICF	Informed Consent Form
ICH	International Council for Harmonisation of Technical Requirements for Pharmaceuticals for Human Use
ISF	Investigator Site File
NHS	National Health Service
NICE	National Institute for Health and Care Excellence
OSOP	One Sheet of Paper
PI	Principal Investigator
PIS	Participant Information Sheet
PPI	Patient and Public Involvement
PPRAG	Patient and Public Research Advisory Group
REC	Research Ethics Committee
SOP	Standard Operating Procedure
TMF	Trial Master File
TMG	Trial Management Group
UoB	University of Birmingham
UHCW	University Hospitals Coventry & Warwickshire
UoW	University of Warwick
WP	Work Package

1. INTRODUCTION

1.1 Background

The scientific community, including healthcare professionals, has called for action to tackle the harm to health from climate change and to aid transition to a sustainable and healthier world ^[1]. The UK is one of the top 20 nations of highest carbon dioxide (CO₂) emissions globally (314 million tonnes of CO₂ equivalent) ^[2]. The National Health Service (NHS) contributes up to 5% of the total UK CO₂ emissions and the NHS Greener plan ^[3] aims to reach net zero carbon emissions by 2040. As Hensher (2020) noted: *“Health care has become an enthusiastic consumer and discarder of plastics, especially since the advent of disposable plastic items as an adjunct for hygiene and infection control”* ^[4]. The COVID-19 pandemic adversely affected NHS emissions due to increased use of personal protective equipment (PPE) and cleaning products. Single-use devices may seem attractive for infection control ^[5, 6] though we need to balance infection control and environmental impact of single-use versus multiple-use devices and equipment.

Endoscopes are a good example of the issues facing sustainable healthcare. Although they are made mainly from plastic (90%), they are traditionally multiple-use devices that are used repeatedly following decontamination after each use ^[7]. There are comprehensive operational procedures for decontamination of endoscopes, but these are resource intensive and require well-trained personnel. Several commercial companies (Ambu, Boston Scientific, Pentax) now market single-use endoscopes and endoscope accessories. These single-use devices are increasingly marketed on the grounds that they reduce the risk of infection and the need for decontamination, but there are concerns about their clinical performance, costs, and environmental impact ^[8-10]. Thus, there is an urgent need to assess the evidence objectively given enthusiasm by Industry to embed single-use endoscopes in practice. There will also be cost implications for less affluent countries thereby widening inequalities in access to diagnostic tests. Importantly, the impact of CO₂ generation in the manufacturing, use and disposable of both single and multiple-use endoscopes must be considered. The findings from this study will thus have international significance and applicability with a drive towards sustainability in healthcare.

Robust evidence is needed to guide policy makers and practitioners to decide whether and under what circumstances single-use endoscopes may be preferred over multiple-use endoscopes. Such evidence needs to take into account clinical outcomes including infection risk, costs and environmental impact, and consider different perspectives, including those of patients and carers, healthcare staff, manufacturers and policy makers. This project aims to address this urgent need for evidence ^[11]. The work needs to be done soon before single-use endoscopes are widely implemented.

Our primary aim is to provide evidence for NHS decision makers on the use of single-use vs. multiple-use endoscopes in gastroenterology, with the following objectives and work packages (WPs):

Work package 1: Review of evidence on technical performance, test accuracy and infection risk of single-use vs multiple-use gastrointestinal (GI) endoscopes, and of literature for other work packages.

Work package 2: Assess costs and consequences arising from use of single-use endoscopes compared to multiple-use ones. It will include specific patient groups (e.g., immunocompromised, those with severe infections) and settings (e.g., intensive care unit) taking into account all factors - costs of purchase, decontamination, consequences of infections and so on.

Work package 3: Assess the wider environmental consequences of a shift to single-use endoscopes including impact on scarce resources for their production and effect of disposal, including landfill and incineration, and the greenhouse gases and waste generated (including transport and storage).

Work package 4: Explore the views of patients receiving endoscopy and staff involved in using, cleaning and decontaminating endoscopes.

Work package 5: Provide evidence for patients, health professionals, service commissioners, manufacturers, environmental management and policy makers to make decisions on single-use and multiple-use endoscopes.

The figure below explains how the WP's come together to form the mixed methods study:

[figure not shown]

Figure 1: Overview of SUMU Endo project structure

1.2 Justification

Research on the environmental impact of various medical devices and procedures is growing ^[12]. Evidence has emerged most notably in surgery and anaesthesia ^[13-15]. A recently published systematic review examined the cost-effectiveness of single versus multiple-use bronchoscopes but did not consider environmental impact ^[16], which was addressed by another study ^[17]. The latter study found that the comparative environmental impact between single-use and reusable bronchoscopes is highly dependent on the cleaning procedures and the use of protective equipment during the disinfection of multiple-use bronchoscopes. A small number of reviews have also examined clinical performance of flexible ureteropyeloscopes ^[18] and endoscopes used in urological procedures. Research on the environmental impacts of single-use versus multiple-use endoscopes remains very limited. The NHS needs high quality evidence on the cost-effectiveness of disposable endoscopes compared to multiple-use ones. Gastroenterology is the largest user of endoscopes with approximately 1.5 million procedures annually in the UK ^[19], and therefore, decisions concerning single-use versus multiple-use endoscopes used in GI tracts could have major clinical, economic and environmental impacts. While evidence is also emerging in this field, we are not aware of any comprehensive evaluation of evidence related to GI endoscopes that cover all these important aspects ^[7]. This proposed research will fill in this important evidence gap.

While the scope of this study is limited to the endoscopes used in gastroenterology, the target is that the methods used to incorporate the views and experiences of patients and staff will be transferable, e.g. to other types of endoscopes and surgical equipment. Similarly, the systematic review (WP1) will search and synthesise literature to identify key considerations and the underlying mechanisms through which various factors may influence the choice between single-use and multiple-use devices, and how these vary by contextual characteristics of person and place. An important output of the project will be a novel system-based logic model ^[20] which depicts the extended endoscope life cycle in the broad ecosystem beyond clinical care pathways. This logic model will be informed by outputs from this study (as well as the other WPs) and will show the mechanisms by which single-use or multiple-use endoscopes influence effectiveness, cost-effectiveness, and environment, and will provide an evidence-based foundation to build on and promote sustainability and the transferability of research findings to other surgical equipment and areas of practice.

Endoscopy is a relatively invasive intervention from the perspective of patients. Patients know they are receiving endoscopy, and often know what the procedure involves and who might do it. However, little information is shared regarding the medical device (the scope) which the clinician uses to perform the intervention. Patients may not be aware that different types of endoscopes are available, with varying environmental profiles. This study is important to understand and work with the degree of risk people having endoscopy are willing to accept, and to understand what additional information people would like, in order

to feel satisfied with different endoscope options. It will be important to determine how the balance between infection control and environmental impact should best be communicated to people in accessible formats.

1.3 Proposed study

This project is taking place as part of Work Package 4 (WP4, see Figure 1). A range of data collection methods will be used to discern the attitudes and experiences of NHS patients receiving endoscopy, and staff working in the NHS who handle colonoscopes and other GI endoscopes before and after use (e.g., selection, procurement, disinfection, and disposal of endoscopes).

1.4 Study population

Patients who have had or are awaiting an endoscope in the NHS will be approached for this study, as well as staff working in the NHS involved in the life cycle of endoscopes.

2 OBJECTIVES

2.1 Primary objective

To explore the views and experiences of patients receiving endoscopy and staff involved in procuring, performing endoscopies, cleaning and decontaminating endoscopes.

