5. ELIGIBILITY CRITERIA

5.1 Inclusion criteria

Patients

- Over the age of 18
- Patient has been invited to an NHS endoscopic clinic to undertake an upper GI endoscope procedure, including diagnostic endoscopies and the less complex therapeutic endoscopy.
- Patient is able to read and understand information provided
- Patient has capacity to provide consent
- Patient is able to participate in an interview.

Staff

- Over the age of 18
- Employed by the NHS
- Working in relevant endoscopy unit - primary work involves the conduct of endoscopy and/or waste disposal services (decontamination or disposal).

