6.2 Recruitment

Patients

We will conduct interviews with patients from 6 hospitals. The PI and research team at each site will identify potential participants through the clinic list. Potential participants who require an endoscopy will be asked if they are interested in the study and given study documentation in person. Alternatively, patients can be sent an invitation letter, PIS and consent form via post and be given at least 24 hours to decide if they would like to take part.

Interested patients can contact the research team using the details provided in the study documents. Alternatively, they will be contacted after a reasonable amount of time has passed with no response to see if they are interested. If they agree to take part, consent will be obtained either in-person at attendance of the clinic, or via the telephone if necessary.

Staff

The PI and research team at each site will generate a list of all staff who work across the endoscopy pathway and identify potential study participants. Participants will be invited to take part in the study via email invitation along with the PIS from the site PI, or informed about the study in person and given a PIS.

Staff will have at least 24 hours to decide if they'd like to take part. If they agree, the PI and research team at site will then contact the member of staff to consent them in-person. Their contact details will be provided to the experienced qualitative researcher after consent who will then organise a focus group consisting of 2-5 members of staff on Microsoft Teams. However if this is not possible, an individual interview will be scheduled. Staff recruitment will continue until all segments of the extended endoscopy care pathway are accounted for, or when saturation is reached in the data collection.

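### The staff population is described inconsistently: the inclusion criterion does not name the procurement staff in the primary objective, the objective does not name disposal staff, and no rule secures coverage of each role

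*Protocol*

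**What the plan says.** The protocol describes the staff population in several places.

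- **Summary, aim:** "staff involved in procuring, using, cleaning and decontaminating endoscopes". The staff objective in the Summary uses the same list.
- **Summary, participants row:** "NHS staff involved in supply chain, decontamination of endoscopes".
- **1.1, Work package 4:** "staff involved in using, cleaning and decontaminating endoscopes".
- **1.3:** staff who handle endoscopes "before and after use (e.g., selection, procurement, disinfection, and disposal of endoscopes".
- **1.4 (study population):** no roles listed; NHS staff concerned with the endoscope life cycle in general.
- **2.1 (primary objective):** "staff involved in procuring, performing endoscopies, cleaning and decontaminating endoscopes".
- **5.1 (inclusion criteria):** NHS employees in the relevant endoscopy unit whose "primary work involves the conduct of endoscopy and/or waste disposal services (decontamination or disposal" services.

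Three further passages govern who is actually recruited. Section 6.1.1 plans 30 staff, 5 from each of 6 sites. It varies staff by age, gender, ethnicity and length of experience, and its example of flexibility is one person covering selection as well as procurement. In 6.2, sites list everyone working along the endoscopy pathway, and "Staff recruitment will continue until all segments of the extended endoscopy care pathway are accounted for"; the same sentence then gives saturation as an alternative end point. Section 6.5 ends the whole study on saturation and does not mention segments.

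**The concern.** In a qualitative study with maximum variation sampling, the definition of who belongs in the sample does the work that a sample size calculation does elsewhere. If the objective, the eligibility criterion and the recruitment rule describe different groups, sites can apply the protocol correctly and still return a sample that does not answer the objective.

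Two mismatches matter here. The objective includes procurement staff, whom the entry criterion does not name. The entry criterion includes disposal staff, whom the objective does not name. The second bears on the project's central contrast. Decontamination is the characteristic after-use step for a multiple-use scope and disposal is that step for a single-use scope, and 3.1 makes perceived risk from both reuse and disposal a key question. Procurement staff, for their part, are involved in choosing between the two types of device. Thin or missing coverage of either group would weaken the staff evidence offered to NHS decision makers.

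**Working it through.** The only arithmetic in the plan is the staff number, and it reproduces: 5 staff × 6 sites = 30. The rest is a comparison of text.

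**Step 1. Roles named in each place.** Section 1.4 is left out because it names no roles.

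| Place | Select/procure | Use/perform | Clean/decontaminate | Dispose |
|---|---|---|---|---|
| Summary, aim | yes | yes | yes | no |
| Summary, participants row | yes (supply chain) | no | yes | no |
| Summary, staff objective | yes | yes | yes | no |
| 1.1, Work package 4 | no | yes | yes | no |
| 1.3 (examples only) | yes | no | yes | yes |
| 2.1, primary objective | yes | yes | yes | no |
| 5.1, inclusion criterion | no | yes | yes | yes |

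Counting down the columns, procurement is named in 5 of 7 places, performing in 5 of 7, cleaning/decontamination in 7 of 7 and disposal in 2 of 7. No row has all four. The Summary aim, the Summary staff objective and 2.1 share one list and the other four rows each differ, which makes five distinct lists.

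**Step 2. Objective against entry criterion.** Section 2.1 has procuring and lacks disposal; 5.1 has disposal and lacks procuring. Because 5.1 controls entry, the disposal omission in 2.1 shuts nobody out. The procurement omission in 5.1 does: a person whose main work is selection, procurement or supply chain does not meet it as worded, and the requirement to work in the endoscopy unit narrows it further. Yet 6.1.1 treats selection and procurement as roles that will be in the sample.

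**Step 3. Is coverage of the eligible roles secured?**

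- Section 5.1 brackets decontamination and disposal together as alternatives, so decontamination staff alone satisfy that part.
- Section 6.2 aims at every segment of the pathway, but no section lists the segments, and the lists in Step 1 disagree.
- Section 6.2 lets saturation end staff recruitment as an alternative to segment coverage, so recruitment may close with a segment empty.
- Role is not among the maximum variation parameters in 6.1.1.

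Eligibility therefore permits performers and disposal staff to be included; nothing requires it.

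**Step 4. Does a coverage requirement fit in 30 places?** With four roles, one participant per role across the six sites together needs 4 of 30 places. Even one per role at every site would need 4 × 6 = 24 of 30, leaving 30 − 24 = 6. The requirement fits on either reading.

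**The case against.** The strongest reply is that summaries, background text and objectives are not recruitment quotas. Section 1.4, headed as the study population, takes in the whole life cycle. Section 5.1 expressly admits those conducting endoscopy and those in disposal. The list in 6.2 covers everyone on the pathway, and recruitment there aims at every segment. The list in 1.3 is only illustrative. On this view the differences are loose drafting and nobody relevant is lost.

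Much of that stands. A reader might infer that the Summary as a whole leaves out those who perform endoscopy; it does not, since its aim and staff objective both include users and only the participants row omits them. A reader might also infer that the primary objective makes disposal staff unnecessary, or that the staff findings will be one-sided. The documents do not support either: 2.1 does not set who must be recruited, 5.1 admits disposal staff, and users and procurers can speak to both kinds of scope.

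Two parts of the reply fail. For procurement, 5.1 is the narrower text, so the breadth of 1.4 and 6.2 does not help: someone listed under 6.2 must still meet 5.1. Dual-role staff whose main work is endoscopy could supply some procurement views, but staff mainly engaged in procurement are not admitted as worded. And the aim of covering every segment does not bind while the segments are undefined and saturation is an alternative end point.

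**Conclusion.** The inconsistency is real and should be corrected. On the wording of 5.1, one of the four roles, selecting/procuring, is not admitted as main work, although the primary objective, the Summary, 1.3 and 6.1.1 expect it. Disposal is eligible but missing from every statement of the aim or objective. Coverage of performers and disposal staff is possible but not secured; the route to an empty segment is the saturation alternative in 6.2, together with the absence of role from the sampling parameters in 6.1.1.

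This does not show that any group will go unsampled. The protocol gives no role mix for the sites and the sampling is purposive, so no probability of missing a role can be derived from it. The conclusion assumes that 5.1 is applied as written and that supply chain in the Summary participants row means acquisition rather than disposal. If supply chain were read to include disposal, that row would change, but the conflict between 2.1 and 5.1 would not.

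**What to change.** 1. Use one staff definition in the Summary (aim, participants row and staff objective), 1.3, 2.1 and 5.1: staff involved in selecting/procuring, performing endoscopy with, cleaning/decontaminating, or disposing of endoscopes. Work package 4 in 1.1 can be aligned at the same time.
2. In 5.1, list decontamination and disposal as separate roles, and word the unit and main-work conditions so that every role in the objective is admitted.
3. In 6.1.1, add role or pathway segment to the maximum variation parameters for staff. Role then has to be recorded; 7.1 names only length of experience as a staff-specific item.
4. In 6.2, tie the segments to this list and require each to be represented across the six sites, within the planned 30, before saturation can close staff recruitment. Section 6.5 should be read consistently with this.

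The cost is wording in eight places (three Summary rows, 1.3, 2.1, 5.1, 6.1.1 and 6.2), plus any alignment of 1.1, 6.5 and 7.1. Changing 5.1 is a change to eligibility, which 10.1 gives as an example of a substantial amendment. No extra participants or visits are needed. The downside is that sites must seek out procurement and disposal staff, leaving slightly fewer of the 30 places for other roles.
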